#### 8.5 Loss to Follow-up

If any of the trial patients are lost to follow up, contact will initially be attempted through the research team at each centre. If the lead investigator at the trial centre is not the patient's usual clinician responsible for their epilepsy care, then follow-up will also be attempted through this latter clinician. Where these attempts are unsuccessful, the patient's GP will be asked to contact the patient and provide follow-up information to the recruiting centre. Wherever possible, information on the reason for loss to follow-up will be recorded.

#### 8.6 Trial Closure

The end of the trial is defined to be the date on which data for all participants is

frozen and data entry privileges are withdrawn from the trial database. However, the trial may be closed prematurely by the Trial Steering Committee (TSC), on the recommendation of the Independent Advisory Group (IAG).

#### 9. STATISTICAL CONSIDERATIONS

#### 9.1 Introduction

Statistical analyses will be performed on each individual trial separately, using SAS version 9.3 (SAS Institute Inc. Cary NC). Trial data will be collected using the EpiNet web-based database, and extracted into SAS for data quality checks and final statistical analysis when all patients have a minimum two year follow-up data at the end of the trial.

All primary analyses of time to 12 month remission from seizures will be on an intention to treat (ITT) basis including all randomised patients regardless of whether they actually satisfied the entry criteria, the treatment actually received, and subsequent withdrawal or deviation from the protocol. Secondary per protocol (PP) analyses will also be undertaken to assess the robustness of ITT analyses. This analysis will include all randomised patients who have taken the prescribed study drug and who do not have major protocol violations. All statistical tests will be two-sided and a 5% significance level maintained throughout the analyses. Confidence intervals for all point estimates will be two-sided 95% intervals.

# 9.2 Sample Size

For each trial, the proposed sample size will provide 90% power at 5% significance level (two-sided) to identify a 10% or greater difference in 12 month disease-free survival at 2 years between the groups, allowing for 10% loss to follow up. This difference is considered to be the minimum clinically important difference. The estimated survival rates were based on 12 month disease free survival at 24 months in the SANAD-1 trials. 67% of patients randomised to lamotrigine and 70% randomised to carbamazepine in SANAD1A achieved the endpoint of 12 months remission of seizures; 78% of those randomised to sodium valproate and 73% of those randomised to lamotrigine in SANAD1B achieved this endpoint (9, 10)

- EpiNet-*First* Trial 1 Patients with focal seizures will be randomised to receive either levetiracetam or lamotrigine or carbamazepine. (489 patients will be required in each arm; 1467 in total.)
- EpiNet-First Trial 2 Patients with generalised seizures (except those with absence seizures only) will be randomised to receive either sodium valproate or levetiracetam. (253 in each arm; 506 in total.)
- EpiNet-First Trial 3 Patients with generalised seizures (except those with absence seizures only), and sodium valproate is deemed unsuitable (e.g. in women of childbearing age), then patients will be randomised to either lamotrigine or levetiracetam. (332 in each arm; 664 in total.)

- EpiNet-*First* Trial 4 Patients with seizures of unknown nature will be randomised to receive either levetiracetam, lamotrigine, or sodium valproate. (392 in each arm; 1176 in total.)
- EpiNet-First Trial 5 Patients with seizures of unknown nature and sodium valproate is deemed unsuitable (e.g. in women of childbearing age), then patients with seizures of unknown nature will be randomised to receive either levetiracetam or lamotrigine. (332 in each arm; 664 in total.)

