# 2.3 Objectives

**EpiNet-First-Trial 1** - To determine whether levetiracetam is more effective than either lamotrigine or carbamazepine when used as monotherapy in patients with untreated focal-onset seizures.

**EpiNet-First Trial 2** - To determine whether levetiracetam is more effective than valproate in patients with untreated generalised-onset seizures. (Patients with absence seizures alone are not included.)

**EpiNet-First-Trial 3** — To determine whether levetiracetam is more effective than lamotrigine in patients with untreated generalised-onset seizures for whom valproate is not suitable. (Patients with absence seizures alone are not included.)

**EpiNet-First-Trial 4** - To determine whether levetiracetam is more effective than lamotrigine or valproate in patients with untreated seizures of uncertain nature.

**EpiNet-First-Trial 5** - To determine whether levetiracetam is more effective than lamotrigine in patients with untreated seizures of uncertain nature, for whom valproate is not suitable.

A full list of outcome measures is presented in section 4.

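### Trials 1 and 4 appear to be sized at two-sided 2.5% per levetiracetam comparison, but the protocol states 5% for the sizing and for every test

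*Protocol*

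**What the plan says.** Protocol section 9.2 makes one statement for all five trials: "For each trial, the proposed sample size will provide 90% power at 5% significance level (two-sided) to identify a 10% or greater difference", with 10% allowed for loss to follow-up. It then gives the sizes. Trial 1 (three arms): "489 patients will be required in each arm; 1467 in total". Trial 4 (three arms): "392 in each arm; 1176 in total". The two-arm trials have 253 per arm (Trial 2) and 332 per arm (Trials 3 and 5).

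Section 2.3 sets two levetiracetam questions in each three-arm trial. For Trial 1 it reads: "To determine whether levetiracetam is more effective than either lamotrigine or carbamazepine". Trial 4 asks the same of levetiracetam against lamotrigine or valproate.

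On the analysis, section 9.1 says: "All statistical tests will be two-sided and a 5% significance level maintained throughout the analyses". It adds: "Confidence intervals for all point estimates will be two-sided 95% intervals". Section 9.5 compares the treatment groups by the log-rank test and fits Cox models with treatment indicators. No section mentions a 2.5% level, a Bonferroni split, an ordering of tests or a global test that must be passed first.

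**The concern.** Trials 4 and 5 show the problem most directly. Both compare levetiracetam with lamotrigine in unclassified seizures, and section 2.2 says their entry criteria differ only in whether valproate is acceptable. Section 9.2 gives them the same power, level and difference. Yet Trial 4 needs 392 per arm and Trial 5 needs 332. Sizing Trial 4 on the valproate rate would make it smaller, not larger, so something that section 9.2 does not state must differ.

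If that is a level halved for two comparisons, the sample size already pays for error control in the three-arm trials, while the analysis text tells the analyst to use 5% and 95% intervals. At stake is the error rate of the primary superiority claims in 1467 + 1176 = 2643 patients.

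**Working it through.** **Inputs (section 9.2).** 90% power; a 10-point difference at 2 years; 10% loss, applied as division by 0.9. Reference rates: lamotrigine 67% and carbamazepine 70% (focal); valproate 78% and lamotrigine 73% (SANAD-1 arm B).

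**Formula (Freedman log-rank, equal arms).** With p2 = p1 + 0.10:
- HR = ln(1 − p2) / ln(1 − p1)
- events for a pair of arms: E = (z_α/2 + z_0.90)² × ((1 + HR)/(1 − HR))²
- n per arm = E / (p1 + p2) / 0.9

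The first factor is 10.507 at two-sided 5% and 12.411 at two-sided 2.5%. Their ratio is 1.181.

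**Two-arm trials at 5%.**
- Trial 2, 78% v 88%: HR 1.400, E = 377.8, n = 377.8/1.66/0.9 = 252.9. Stated: 253.
- Trials 3 and 5, 73% v 83%: HR 1.353, E = 466.1, n = 466.1/1.56/0.9 = 332.0. Stated: 332.

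The formula therefore reproduces the protocol's own figures for the two-arm trials.

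**Three-arm trials.**

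| Trial | Rates | n at 5% | n at 2.5% | Stated |
|---|---|---|---|---|
| 1 | 67% v 77% | 535.96/1.44/0.9 = 413.5 | 633.06/1.44/0.9 = 488.5 | 489 |
| 4 | 73% v 83% | 466.13/1.56/0.9 = 332.0 | 550.58/1.56/0.9 = 392.2 | 392 |

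Solving for the level that gives 90% power at the stated size returns 0.0249 (Trial 1), 0.0250 (Trial 4), 0.0499 (Trial 2) and 0.0500 (Trials 3 and 5). The ratio 392/332 = 1.181 equals the ratio of the two first factors.

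**Alternatives tried.** A split over three pairs (1.67%) gives about 532 and 427, so it does not fit. At 5%, a 10-point fall from 70% to 60% gives 487.8, about one patient from Trial 1's 489, but the same fall gives 402 against 253 in Trial 2 and 460 against 332 in Trial 3. Unpooled proportions at 5% with n × 1.1 give 392 for Trial 4, but also 392 for Trials 3 and 5 (stated 332). No single method tried at 5% fits all five trials.

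**If 5% is taken literally.** Power at the stated sizes is 94.1% in both trials. The requirement would be 3 × 414 = 1242 in Trial 1 and 3 × 332 = 996 in Trial 4, that is 225 and 180 fewer than stated.

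**Error rates.** The two comparisons share the levetiracetam arm, so with equal arms their statistics have correlation 0.5 under the null. For two pairwise tests with no gate:

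| Level per comparison (two-sided) | At least one rejection, either direction | At least one false claim that levetiracetam is superior |
|---|---|---|
| 5% | 9.1% | 4.5% |
| 2.5% | 4.6% | 2.3% |

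**Power after the split.** At 2.5% per comparison, 489 per arm gives 90.0% (67% v 77%) and 392 per arm gives 90.0% (73% v 83%).

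**The case against.** **The 5% may be meant per trial.** On that reading a 2.5% split is how 5% family-wise is delivered, and 489 and 392 agree with section 9.2. This is plausible as the designers' intent. It does not rescue the text, because section 9.1 applies 5% to all statistical tests and 95% to all point estimates, with no exception for pairwise comparisons.

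**Section 9.5 names only a log-rank test between the groups.** In a three-arm trial that may be a global three-group test. If pairwise tests followed only after it rejected at 5%, simulation puts the chance of any false levetiracetam rejection at about 4.2%, not 9.1%. This stands as a limit on the error figure. The protocol states no such gate, and does not exclude one.

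**A stronger reading is tempting:** that levetiracetam gets two chances at 5% each to be declared superior, so that the main claim has a 9% false-positive rate. The documents do not support this. The tests are two-sided, so each gives a 2.5% chance of a false superiority claim, and together about 4.5%. The 9.1% also counts false findings that levetiracetam is worse. The near-doubling, from 2.5% to 4.5%, does stand.

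**The level may be left to the SAP.** Section 9.5 promises a SAP for each trial, and silence on multiplicity would be no finding. But the protocol is not silent: a SAP that split the level would contradict section 9.1, and one that did not would discard what the sizes appear to pay for.

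**The 2.5% is an inference.** This is correct, and it should be presented as one.

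**Conclusion.** Section 9.2's single statement of 90% power at two-sided 5% does not describe Trials 1 and 4. Their sizes fit two-sided 2.5% per levetiracetam comparison to within one patient, by the same formula that fits the other three trials at 5%. Taken at 5%, they would have about 94% power and be 225 and 180 patients larger than required. That rests on the Freedman formula, the quoted SANAD-1 rates and a 10-point rise over lamotrigine.

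Section 9.1 does not carry the split into the tests or intervals. The resulting family-wise error of about 9.1% (about 4.5% for false superiority) is conditional on two ungated pairwise tests at 5% and equal arms. It is not a property that the protocol fixes.

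**What to change.** - **Section 9.2:** state that Trials 1 and 4 are sized for 90% power at two-sided 2.5% per levetiracetam comparison, for a 10-point advantage of levetiracetam over the lamotrigine rate (67% in Trial 1, 73% in Trial 4).
- **Sections 9.1 and 9.5:** for Trials 1 and 4, state that the primary analysis is two pairwise log-rank tests, levetiracetam versus each comparator, at 2.5% each or by Holm at family-wise 5%. Give matching intervals: 97.5% for the 2.5% split.
- Keep 5% and 95% intervals for Trials 2, 3 and 5.

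The sponsor should confirm that 2.5% was the level used.

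**Cost.** Wording only; 489 and 392 per arm stay. Each comparison faces a stricter threshold (critical value 2.24 in place of 1.96 under the equal split), and planned power is 90% where the text as written would give about 94%. The 90% holds for a 10-point levetiracetam advantage. For a 10-point deficit in Trial 1 it would be about 82% (67% v 57%) to 84% (70% v 60%), so section 9.2 should give the direction.

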#### 9.3 Outcome Measures

See section 4.

# 9.4 Interim Monitoring and Analyses

Recruitment rates will be reviewed regularly, and annual progress reports regarding patient recruitment will be prepared and forwarded to the Independent Advisory group and appropriate ethics committees. No interim analysis is planned.

# 9.5 Analysis Plan

All participants who are invited to participate in EpiNet-First trials will be accounted for and a CONSORT statement prepared. A table summarizing the number of participants who have assessed for eligibility, registered in each trial and been randomized for participation, will be provided. Participant disposition will be presented in one or more figures.

Demographic data collected on all randomised participants will be summarized. Summaries of continuous variables which are normally distributed will be presented as means and standard deviations or medians and inter-quartiles for skewed data, while categorical variables will be presented as frequencies and percentages.

Treatment evaluations will be undertaken for each trial separately. The primary outcome will be summarised by Kaplan-Meier curves and compared between the treatment groups using the log rank test. Cox proportional hazards regression models will be used in two different ways: (i) including the treatment effect only, using treatment indicator variables (ii) including the treatment effect together with stratification factors and important baseline covariates. The impact of country effect on the treatment comparison will be controlled by considering a random effect in the regression analysis. A similar analysis strategy will be employed for the other secondary time to event outcomes. For time to treatment failure, further analysis will be undertaken to assess the two main reasons for treatment failure-inadequate seizure control and unacceptable adverse effects. To allow for possible dependence between the different withdrawal risks, cumulative incidence analyses will be presented(39).

The proportion of patients who achieve a 12 month remission by 18 months who have not changed to a different AED will be compared between treatment groups using simple chi-squared test with estimation of relative risks and 95% confidence EpiNet-First Study Protocol Version 1.0 Dated 15/04/14

intervals. Logistic regression analysis will also be conducted adjusting for stratification factors and important baseline covariates.

QOL data will be analysed longitudinally to explore between treatments differences in scale scores overtime, taking account of stratification factors, baseline QOL and other important covariates. Line listings will be prepared for all serious adverse events.

A full Statistical Analysis Plan (SAP) will be developed by the project statistician prior to the final analysis of each trial. The SAP will be agreed by the TSC before being sent to the IAG for comment and approval.

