#### 6.3 Randomisation

Patients **should not** be randomised until:

- a) Consent has been obtained from the patient (parent / legal representative where the patient is under 16 years of age)
- b) The minimum baseline data has been recorded into the EpiNet record;
- c) Eligibility criteria have been fulfilled.

The trial in which the patient will be enrolled will be determined by the seizure type and the willingness of the patient to take valproate. Investigators will be guided through this process by algorithms within the EpiNet database. Investigators will be asked what type of seizures the patient has, and whether the patient would be willing to take valproate. Patients will then be randomised to one of the following treatments:

For each of the trials, randomisation will be by block randomisation with variable block size to minimize any potential for predicting allocation. Randomisation will be stratified by country, age (below 18 vs 18 or older) and sex.

Patients who have focal seizures will be entered into the **EpiNet-First Trial 1**, and randomised to receive either levetiracetam or lamotrigine or carbamazepine (in a 1:1:1 ratio).

Patients who have generalised seizures (excluding patients who have a focal onset to their seizures, or who have absence seizures alone) who are willing to take valproate will be entered into the **EpiNet-First Trial 2** and randomised to receive either levetiracetam or valproate (in a 1:1 ratio),

Patients who have generalised seizures (excluding patients who have a focal onset to their seizures, or who have absence seizures alone) who are NOT willing to take valproate will be entered into the **EpiNet-First Trial 3** and randomised to receive either levetiracetam or lamotrigine (in a 1:1 ratio)

Patients who have seizures of uncertain nature who are willing to take valproate will be entered into the **EpiNet-First Trial 4** and randomised to receive either levetiracetam or lamotrigine or valproate (in a 1:1:1 ratio).

Patients who have seizures of uncertain nature who are NOT willing to take valproate will be entered into the **EpiNet-First Trial 5** and randomised to receive either levetiracetam or lamotrigine (in a 1:1 ratio).

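### Randomisation is stratified by country, age group and sex, but the test named for the primary outcome ignores these factors, and section 9.5 does not say which of its three analyses decides the result

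*Protocol*

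**What the plan says.** Section 6.3 (Randomisation) sets the same scheme for every trial: "Randomisation will be stratified by country, age (below 18 vs 18 or older) and sex", with blocks of varying size.

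Section 9.5 (Analysis Plan) names the comparison for the primary outcome, time to 12-month remission: "The primary outcome will be summarised by Kaplan-Meier curves and compared between the treatment groups using the log rank test". No strata are attached to that test. Cox regression follows in two forms: "(i) including the treatment effect only, using treatment indicator variables" and "(ii) including the treatment effect together with stratification factors and important baseline covariates". The next sentence deals with country: "The impact of country effect on the treatment comparison will be controlled by considering a random effect in the regression analysis".

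Section 9.1 sets the error rate: "All statistical tests will be two-sided and a 5% significance level maintained throughout the analyses". Section 9.2 claims 90% power to detect a 10-point difference at two years, after 10% loss. Section 9.5 ends by deferring detail to a full SAP, which need only exist before the final analysis of each trial.

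**The concern.** Stratified randomisation balances the arms on country, age group and sex. If these factors predict remission, that balance makes the true variance of the treatment comparison smaller than the variance an unstratified log-rank test assumes. The test then rejects too rarely under the null and gives up power that a test using the factors would keep. Country is a plausible prognostic factor: section 2.1 lists users of the database from 20 countries with very different health systems.

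The second problem is ranking. Section 9.5 leads to up to three answers for one primary question: plain log-rank, treatment-only Cox and adjusted Cox. The plain log-rank is named first, but nothing says that it decides. The trials are open-label (section 7.4) and the SAP may be written late, so the choice could be settled after outcome data have accrued.

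**Working it through.** **1. Which test do the planned sizes belong to?** Inputs from section 9.2: remission at 24 months of 67% (lamotrigine, focal), 73% (lamotrigine, SANAD-1 B) and 78% (valproate); a 10-point gain; 90% power; 10% loss. Formulas for an unstratified log-rank test (Freedman):

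- HR = ln(1 − p1)/ln(1 − p0), with p1 = p0 + 0.10
- events D = (z_α/2 + z_β)² × [(HR + 1)/(HR − 1)]²
- per arm n = D/(2 × mean remission probability), rounded up, then divided by 0.9

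| Trial | p0 → p1 | HR | α used | D | n per arm | ÷ 0.9 | Stated |
|---|---|---|---|---|---|---|---|
| 1 | 67 → 77% | 1.326 | 0.025 | 633 | 440 | 488.9 | 489 |
| 2 | 78 → 88% | 1.400 | 0.05 | 378 | 228 | 253.3 | 253 |
| 3 and 5 | 73 → 83% | 1.353 | 0.05 | 466 | 299 | 332.2 | 332 |
| 4 | 73 → 83% | 1.353 | 0.025 | 551 | 353 | 392.2 | 392 |

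For Trial 3: HR = ln 0.17/ln 0.27 = 1.353; D = 10.507 × (2.353/0.353)² ≈ 466; n = 466/(2 × 0.78) ≈ 298.8, so 299; 299/0.9 = 332.2. All five sizes reproduce. The 0.025 for the three-arm trials is inferred, because the text states only 5%. The planned 90% is therefore the power of the unstratified test itself.

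**2. Strata effects assumed.** The protocol gives none, so a range is used:

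| Scenario | SD of country log-hazard | Age HR | Sex HR |
|---|---|---|---|
| None | 0 | 1 | 1 |
| Mild | 0.2 | 1.2 | 1.1 |
| Moderate | 0.35 | 1.4 | 1.15 |
| Strong | 0.5 | 1.75 | 1.3 |

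Each was simulated with 10 and with 20 countries at Trial 3 size: 332 per arm, 10% loss, censoring at 24 months, permuted blocks of 4 or 6 within country × age × sex.

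**3. Planned HR of 1.353 taken as holding within strata.** Power in %, 2000 runs per setting (about ±1.5 points), for 10 / 20 countries:

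| Scenario | Plain log-rank | Cox stratified by country, with age and sex | Log-rank on every cell |
|---|---|---|---|
| None | 91.2 / 92.8 | 90.2 / 92.2 | 88.7 / 88.9 |
| Mild | 90.8 / 91.2 | 91.4 / 91.6 | 89.4 / 87.1 |
| Moderate | 89.0 / 88.2 | 91.8 / 90.3 | 89.6 / 86.8 |
| Strong | 84.9 / 82.8 | 90.8 / 89.7 | 88.4 / 86.5 |

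Second column minus first: −1.0 / −0.6 (none), +0.6 / +0.4 (mild), +2.8 / +2.1 (moderate), +5.9 / +6.9 (strong). Type I error of the plain log-rank was 4.2 / 3.5% (moderate) and 3.6 / 3.3% (strong); the country-stratified Cox model stayed at 4.3–5.4%. A separate run of country stratification gave −1.5 to +1 points (none or mild), about +2 (moderate) and +5 to +6 (strong).

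**4. Planned 73% versus 83% taken as marginal rates.** Here the strata do not dilute the overall difference. The plain log-rank kept 88.9–91.4% power in every scenario. A log-rank on every country × age × sex cell gained about 3 points only with strong effects (91.4 to 94.3%; 91.1 to 93.7%). It lost up to about 4.5 points with no effects and 20 countries (89.1 to 84.6%), because 20 × 2 × 2 = 80 cells are too sparse. Type I error of the plain test was 4.6–5.1% (none or mild) and 3.2–4.3% (moderate or strong).

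**The case against.** The strongest reply has four parts.

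- **Power.** A reader might infer that the trials fall short of 90%. The documents do not support that. The sizes were evidently computed for the unstratified log-rank, and if the 10-point difference is marginal that test keeps about 90% in every scenario tried. The shortfall in step 3 arises only if 1.353 is the effect within strata and the strata are clearly prognostic. This part stands.
- **Validity.** An unadjusted primary test with adjusted support is a recognised choice, and its error here is on the safe side: a type I error of 3–4% does not undermine a positive result. This stands too; the cost is efficiency.
- **Already planned.** Section 9.5 contains the adjusted Cox model and the country random effect. That is true, and it makes the change cheap. But the model is listed as one of several uses of Cox regression, and nothing gives it the deciding role.
- **SAP detail.** A SAP, agreed by the steering committee and approved by the advisory group, could settle the ranking, and section 9.4 plans no interim analysis. This is fair as to detail. However, the protocol itself names an unstratified test, so a SAP that made another analysis decisive would depart from the protocol's wording.

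Stratifying on every cell can lose power. That counts against one form of remedy and does not touch the one proposed below.

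**Conclusion.** The point holds as a matter of efficiency and clarity. Randomisation uses three factors, the test named for the primary outcome uses none, and section 9.5 does not say which of its three analyses decides.

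At Trial 3 size, with HR 1.353 within strata, the plain test gives up about 2 to 3 points of power under moderate assumed strata effects and about 5 to 7 under strong ones, and its type I error falls to about 3–4% under strong effects. With no or mild effects the two approaches differ by no more than about 1.5 points in either direction. These sizes rest on assumed strata effects and country numbers, which the protocol does not give. The random-effect version of the adjusted model was not simulated; the figures are for stratification by country. It should not be concluded that the stated 90% is wrong or that the log-rank test is invalid.

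**What to change.** In section 9.5, name one deciding analysis of the primary outcome for each trial: the Cox model already planned, with treatment, age group, sex and a country random effect, and without the further baseline covariates, which are not named. An equally good choice is a Cox or log-rank test stratified by country, with age group and sex as covariates in the Cox form. Fix the rule for pooling small countries before outcome data are reviewed. Do not stratify on every country × age × sex cell.

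Label the unstratified log-rank and the treatment-only Cox as supportive, and keep the Kaplan-Meier curves as the description. State that the reported hazard ratio is the one within strata, and say in section 9.2 whether the 10-point difference is meant as marginal.

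The change is wording only: all three factors must be known to randomise a patient. The downside is a loss of at most about 1–2 points of power if the strata turn out not to be prognostic.

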The LaLiMo study was conducted to test the superiority of levetiracetam over lamotrigine in patients with either focal or generalised seizures (19). There was no difference in the primary endpoint - the rate of seizure-free patients at 6 weeks - or the secondary endpoints. However, sodium valproate was not included in this trial, and 40% of the patients had protocol violations. Fewer than 10% of the patients included were children, and none were aged less than 12 years. Twenty per cent of the patients had experienced only a single seizure, and these patients had a lower relapse rate than those patients who had had 2 or more seizures. In addition, this study did not assess sustained seizure-freedom.

Zonisamide is included in Arm A of the SANAD-11 trial (i.e. the SANAD-11 trial for patients with focal seizures.) Zonisamide is not included in EpiNet-*First* Trial 1 since it is not marketed in many of the countries in which the EpiNet-*First* trials are being undertaken.

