# 6.2 Baseline

Once consent has been obtained from the patient (or parent / legal representative where applicable, and assent by the child where appropriate and applicable) the delegated member of the research team e.g. research nurse/consultant should record the required baseline data (which will include seizure history, history of neurological insult, febrile seizures, family history of epilepsy, EEG and imaging (CT or MRI) results) into the EpiNet record. If further investigations (EEG or imaging) are requested at this visit, data on results will be collected when available, but randomisation need not be delayed. If the patient is confirmed eligible then the research team should proceed to randomise the patient.

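### Section 9.5 compares the primary outcome with an unadjusted log-rank test and leaves the status of the covariate-adjusted Cox model open: some efficiency is forgone, but power does not fall below target

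*Protocol*

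**What the plan says.** Protocol section 9.5 gives the comparison of the primary outcome in one sentence: "The primary outcome will be summarised by Kaplan-Meier curves and compared between the treatment groups using the log rank test". It then plans two Cox models, the first with treatment only and the second "ii) including the treatment effect together with stratification factors and important baseline covariates". It adds: "The impact of country effect on the treatment comparison will be controlled by considering a random effect in the regression analysis". It does not say which of these results decides the trial, and it does not name the covariates.

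Section 6.2 lists the "baseline data (which will include seizure history, history of neurological insult, febrile seizures, family history of epilepsy, EEG and imaging" results to be entered, and lets randomisation go ahead while further EEG or imaging results are awaited. Section 6.3 makes recording part of this set a condition of randomisation: "The minimum baseline data has been recorded into the EpiNet record". It also fixes the strata: "Randomisation will be stratified by country, age (below 18 vs 18 or older) and sex". Seizure history and neurological insult are therefore balanced between arms only by chance.

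The closest the protocol comes to evidence of prognostic value is in section 2.2, in the Trial 1 rationale. It says of single-seizure patients in an earlier lamotrigine-levetiracetam trial that "these patients had a lower relapse rate than those patients who had had 2 or more seizures".

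**The concern.** The named test ignores the factors that randomisation is stratified on, and all the clinical history taken before allocation. In a time-to-event model, leaving out a prognostic covariate pulls the treatment hazard ratio towards 1 and costs power. A chance imbalance in such a covariate is also carried into the unadjusted result. Section 9.5 already plans an adjusted model, so the question is which of the planned results is the primary one. That matters more because treatment is open-label (section 7.4): three results on the same endpoint with no stated order leave room to choose among them later.

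**Working it through.** **1. Which test were the trials sized for?** Inputs from section 9.2: reference proportion p0 in remission by 2 years (lamotrigine 67% in Trial 1; valproate 78% in Trial 2; lamotrigine 73% in Trials 3, 4 and 5), p1 = p0 + 0.10, 90% power, 10% loss. The choice of reference arm is inferred from the match.

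Formulas (Freedman, unadjusted log-rank):
- HR = ln(1 − p1) / ln(1 − p0)
- events D = (z_alpha + z_power)² × [(HR + 1)/(HR − 1)]²
- patients per arm = D / (p0 + p1) / 0.9

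| Trial | Two-sided alpha | HR | D | Per arm | Stated |
|---|---|---|---|---|---|
| 1 | 0.025 | 1.3256 | 633.1 | 488.5 | 489 |
| 2 | 0.05 | 1.4003 | 377.8 | 252.9 | 253 |
| 3 and 5 | 0.05 | 1.3533 | 466.1 | 332.0 | 332 |
| 4 | 0.025 | 1.3533 | 550.6 | 392.2 | 392 |

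Example, Trial 3: ln(0.17)/ln(0.27) = 1.3533; (1.960 + 1.282)² = 10.507; 10.507 × (2.3533/0.3533)² = 466.1; 466.1/1.56 = 298.8; 298.8/0.9 = 332.0.

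All five sizes reproduce, so the unadjusted log-rank test is evidently the design test, and at the stated sizes it has 90.0% power. (Trials 1 and 4 match only at 0.025 per comparison. At 0.05 they would need about 414 and 332 per arm. That is a side observation.)

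**2. What would adjustment add?** The protocol gives no prognostic strength, so it is an assumption: one normally distributed baseline score with SD between 0 and 1.0 on the log-hazard scale. Simulation, 2,000 trials per setting: stated sizes, the two-year proportions held at p0 and p1, 10% of patients removed, cut-off at 2 years, and the alpha levels above. Each cell shows log-rank power, then adjusted Cox power.

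| SD | Trial 1 | Trial 2 | Trial 3 (and 5) | Trial 4 |
|---|---|---|---|---|
| 0 | 90.3 / 90.3 | 91.2 / 91.0 | 91.0 / 90.9 | 90.1 / 89.8 |
| 0.3 | 90.5 / 92.8 | 92.4 / 94.3 | 91.3 / 93.1 | 90.8 / 92.9 |
| 0.5 | 91.5 / 96.3 | 93.0 / 97.6 | 91.9 / 96.8 | 93.3 / 97.3 |
| 0.7 | 93.2 / 99.3 | 94.9 / 99.4 | 93.4 / 99.3 | 94.2 / 99.2 |
| 1.0 | 94.4 / 99.9 | 94.9 / 100.0 | 95.4 / 100.0 | 94.2 / 100.0 |

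The gain is none at SD 0, about 2 points at 0.3 and 4 to 5 points at 0.5. Above that it is about 5 to 6 points, limited because adjusted power is then close to 100%. Simulation error on a power near 92% is √(0.92 × 0.08/2000), about 0.6 points, so the differences at SD 0 are noise. At SD 0.5 in Trial 3 the chance of missing a true 10-point difference falls from about 8% to about 3%. The attenuation is visible too: in Trial 3 the hazard ratio conditional on the score is 1.428 at SD 0.5, against 1.353 when the score has no effect.

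**3. Ties at month 12.** Time runs from randomisation (section 4.1), so nobody can reach the endpoint before month 12 and many may reach it exactly then. A check for Trials 3 and 5, assuming about 40% of control patients remit at month 12 (Efron ties, 600 runs), gave 90% against 91% at SD 0.3, 91% against 96% at SD 0.5, and 90% against 98% at SD 0.7. The pattern persists.

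**The case against.** The strongest reply is that nothing here is invalid. A log-rank test with supporting Cox models is conventional, the trials were sized for it, and it meets the 90% target. That stands. A reader might infer from the power comparison that the trials are underpowered; step 1 shows that they are not.

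A second reply is that adjustment is already planned in the next sentence of 9.5, and that a later SAP, which 9.5 promises, can rank the analyses and list the covariates. The first half stands: it would be wrong to say that baseline imbalance goes unaddressed. The second half stands for the covariate list. It does not remove the point, because the protocol itself names the log-rank test as the between-group comparison, and changing that is a choice rather than a missing detail.

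A third reply concerns prognostic strength. It is tempting to call the baseline values strong predictors, but the protocol does not support that. The cited comparison is of one seizure against two or more, and section 5.1(c) requires at least two, so that contrast cannot arise among eligible patients. Hence the range starting at SD 0.

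A fourth is availability. Section 6.2 says seizure history but names neither a seizure count nor a date of first seizure, the minimum baseline set in 6.3 is not defined, and Table 1 marks the medical-history review as indicated or appropriate. The gain therefore cannot be called free until the record is checked. Counting seizures also needs a rule in Trial 2, which admits patients with myoclonic seizures only.

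Finally, the simulation uses one complete, correctly specified score under proportional hazards, which favours adjustment.

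**Conclusion.** The point holds as an efficiency improvement with a wording-only remedy. The primary comparison named in 9.5 is unadjusted, and the adjusted model beside it has no stated status. At the stated sample sizes, adjustment would add 0 to about 5 points of power for an assumed log-hazard SD of 0 to 0.5, and somewhat more if the covariates are stronger, from a base that already meets 90%. The size rests wholly on that assumed SD, on proportional hazards and on complete covariate data. It is not a validity failure or a shortfall in sample size.

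**What to change.** In section 9.5, state that the primary treatment test and hazard ratio come from Cox model (ii), and list its terms in advance:
- the stratification factors: country (through the random effect already planned), sex, and age as a continuous term;
- prior neurological insult (yes/no);
- one pre-specified seizure-history measure recorded before allocation, for example the log number of seizures if the EpiNet baseline record holds it, with a counting rule for myoclonic and absence seizures.

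Use only values recorded before allocation. Exclude EEG and imaging results, which section 6.2 allows to arrive after randomisation. Keep the unadjusted log-rank test and hazard ratio as supporting analyses.

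The cost is wording, plus a check of what the baseline record contains, settled before outcome data by arm are seen. No patients or visits are added, and the sample sizes can stand. The small downside is that the primary hazard ratio becomes conditional on the covariates, which is why the unadjusted one is reported beside it.
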